#### 8. STATISTICAL CONSIDERATION AND DATA ANALYSIS PLAN

#### 8.1 Analysis of baseline characteristics

To determine the demographics and characteristics of the patients in the two arms the following data will be collated:

- Age
- Gender

- BMI
- Smoking status
- Type of lymphoedema:
- Lymphoedema severity (0 indicating currently no edema symptoms and 3 indicating the worst possible stage, according to the classification of the International Society of Lymphology. International Society of Lymphology. The diagnosis and treatment of peripheral lymphedema. 2009 Consensus Document of the International Society of Lymphology. Lymphology 2009;42(2):51e60.
- Clinician's lymphoedema severity score
- Lymphoedema chronicity
- Type of compression used (or other type of bandaging, dressing and/or hosiery) prescribed for index leg(s)
- Leg elevation habits
- Significant comorbidities, including, (history of) cancer, diabetes, rheumatoid arthritis, heart failure, hypertension, CKD.
- Vascular profile of legs: presence of chronic venous insufficiency, peripheral arterial disease, venous, mixed or arterial leg ulcer, diabetic foot ulcer.

Any differences in distribution will be established with Chi-squared test or ANOVA as indicated.

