## **RESEARCH PROTOCOL SUMMARY**

TITLE:	PEDAL; Plantar Exercise, Daily, for Lymphoedema, a single- centre, controlled, prospective, randomized feasibility trial			
Short title:	PEDAL trial			
IRAS number	265968			
Device description Study design	StepIt plantar flexion rocker pedal device. CE-marked and licensed medical device. To be used in this study for indicated purpose, namely plantar flexion exercise.Multi centre, controlled, prospective randomized feasibility			
	trial			
Primary objective	To assess the feasibility of conducting a full RCT in the future			
	
 
Participants' compliance to StepIt exercise regime and total number of steps achieved
 
Recruitment and attrition rates, willingness of patients to be randomised, response rates to questionnaires, and degrees of missing data
 
Testing of eligibility criteria and ability/willingness of clinical staff to partake in recruitment of participants
 
Adequacy of duration of follow-up (e.g. in relation to lymphoedema status)
 
			
Secondary objectives	To determine the acceptability and efficacy of the step-it pedal as an adjuvant therapy for leg lymphoedema at 6 and 12 weeks post-baseline			
	
 
Efficacy of StepIt pedal adjunct therapy vs standard care. Status leg volume difference.
 
Ankle circumference
 
Ankle range of motion
 
Lymphoedema-related quality of life
 
General quality of life
 
Patient feedback on use of the device (StepIt users only)
 
			
Patient population	A total of 24 participants, over the age of eighteen, with leg lymphoedema managed by the community lymphoedema team. Participants must have the capacity to provide informed written consent and complete patient reported outcome measures. Participants are recruited from the local Hospice at Home lymphoedema service caseload.			

	
 
12 Patient will receive treatment as usual (TaU)
 
12 Patients will receive TaU plus StepIt exercise programme intervention
 
			
	Randomisation will not be stratified.			
Sponsor	North Cumbria Integrated Care NHS Foundation Trust			
Manufacturer & funder	StepIt System AB, [name] Contact: [name], PhD, [contact]			
	[contact]			
Chief Investigator	[name], GPwSI Research, North Cumbria Integrated Care NHS Foundation Trust, R&D Department, [name] [contact]			
Co-investigators				

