#### 6. SUBJECTS

#### 6.1 Anticipated number of research subjects

This concerns a feasibility trial, and therefore the results from this study should inform a potential effect size for StepIt pedal exercise therapy, and also the degree in variance in lymphoedema volume changes (primary clinical outcome). To date, there is not sufficient published data to gain an insight in the effect that calf muscle exercise may have on lymphoedema symptoms. Guidance from a publication by Julious (2005) advises the use of 12 participants per treatment arm, and this approach will be taken here (see Table 5). Patient withdrawal rates before week 12 are not known at present and measuring this will be a primary aim

Table 5, sample size numbers required, based on hypothetical differences between published data and study outcomes

	Standard (control) arm	care	Standard care plus Steplt pedal arm
Patients (n)	12		12

Since this concerns a randomised controlled trial, albeit in the shape of a feasibility study, reprting will be done in line with CONSORT guidelines (Schulz, Altman & Moher 2010). The number of patients screened but who did not meet the inclusion criteria or who declined to participate will be recorded, as will any patients who are lost to follow-up (Appendix 2).

The patient attrition rate (withdrawal and loss to follow-up) will also be recorded, since this involves a study with at multiple visits, albeit incorporated into standard clinical appointments. Patients will be recruited from the adult (age 18+) population routinely seen by the evaluating clinical staff members.

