#### 6.1.1 Randomisation

A 1:1 allocation to the control and intervention group respectively will be applied. Following written consent patients will be allocated at random to the control or intervention group, using a non-restricted randomised sequence generated for the whole sample using a free ware randomisation programme, see https://www.randomizer.org/. Sequential envelopes with each next randomisation allocation will be used to achieve concealment.

The researcher/lymphoedema care specialist will inform the patient what arm they have been allocated. As the study involves the Clinical Lymphoedema Specialist or Researcher consenting and following up patients and a self-administered intervention of necessity it is not possible to achieve blinding for the participants or the Clinical Lymphoedema Specialists.

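### Section 8.1 uses significance tests to establish baseline differences between randomised arms; at 12 per arm they can neither establish nor rule out an imbalance that matters

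*Protocol*

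**What the plan says.** Protocol section 8.1 introduces its list with "To determine the demographics and characteristics of the patients in the two arms the following data will be collated". The list has 12 bullets. Ten are single characteristics: age, gender, BMI, smoking, type of lymphoedema, two severity scales, chronicity, compression and leg elevation. The other two bullets name six comorbidities and six vascular or ulcer conditions. The section closes with "Any differences in distribution will be established with Chi-squared test or ANOVA as indicated".

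Section 6.1.1 states "Following written consent patients will be allocated at random to the control or intervention group", using a "non-restricted randomised sequence generated for the whole sample" and sequential envelopes. The protocol summary adds "Randomisation will not be stratified". Section 6.1 sets the size: it "advises the use of 12 participants per treatment arm, and this approach will be taken here".

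Section 8.2 compares the change in leg volume from week 0 to week 12 by a Mann-Whitney test. Section 8.3 allows a Mann-Whitney or t-test for leg volume. Neither takes a covariate. The covariates for the possible Cox model in section 8.3 are named in advance.

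**The concern.** A significance test asks whether an observed difference could have arisen by chance. With random allocation that answer is already known: apart from a failure of the allocation process, chance is the only explanation. A small p-value is then a chance finding, and a large one does not show that the arms are comparable. Whether an imbalance matters depends on its size and on how strongly the characteristic predicts leg volume. The test measures neither.

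At stake is how the results are read. In an unstratified trial of 24 people with an unadjusted leg-volume comparison, readers will use the baseline table to judge whether the arms were alike. Labels of different or not different drawn from these tests could mislead them in both directions.

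**Working it through.** The protocol gives no significance level, power or error rate for these tests, so there is no stated figure to reproduce.

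**Inputs**
- Arms: 12 and 12 (sections 6.1 and 6.1.1).
- Number of tests k: 12 if each bullet is tested once; 10 + 6 + 6 = 22 if each named condition is tested separately (section 8.1).
- Significance level: not stated; 0.05 two-sided assumed, with 0.01 and 0.10 shown as a range.

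**1. Chance of at least one significant result when nothing but chance operates**

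Formula, for independent tests each of exact size α: 1 − (1 − α)^k.

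| α | k = 12 | k = 22 |
|---|---|---|
| 0.01 | 11% | 20% |
| 0.05 | 1 − 0.95^12 = 46% | 1 − 0.95^22 = 68% |
| 0.10 | 72% | 90% |

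The expected number of chance findings at 0.05 is 12 × 0.05 = 0.6 or 22 × 0.05 = 1.1.

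**2. Allowance for small cells**

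With 12 per arm the expected count in a cell is 12 × prevalence, which is below 5 when prevalence is under 5/12 = 42%. Enumerating all 12 v 12 tables gives the exact size of the uncorrected 2 × 2 Chi-squared test at a nominal 5%:

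| Prevalence | 5% | 10% | 20% | 30% | 50% |
|---|---|---|---|---|---|
| Exact size | 0.2% | 1.5% | 3.9% | 4.9% | 6.4% |

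With the Yates correction the size is at most 2.3% at these prevalences.

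The protocol gives no prevalences. If the 12 named conditions have sizes between 1.5% and 3.9% and the other 10 tests have 5%, the 22-item figure becomes:
- 1 − 0.95^10 × 0.985^12 = 50%
- 1 − 0.95^10 × 0.961^12 = 63%

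A simulation with 3,000 runs per setting used 3 continuous and 7 categorical variables, with or without 12 binary conditions, at assumed prevalences of 5% to 50%. It gave 40% (10 variables) to 58% (22 variables) uncorrected, and 32% to 40% with Yates correction.

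**3. What a non-significant result hides**

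For two arms, ANOVA is equivalent to the t-test with 22 degrees of freedom. The smallest standardised difference reaching p < 0.05 is t(0.975, 22) × √(1/12 + 1/12) = 2.074 × 0.408 = 0.85 SD.

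The chance that the observed difference is 0.5 SD or more, by randomisation alone, is P(|t22| > 0.5/0.408) = 23%. Of that, 5 percentage points lie beyond 0.85 SD and are flagged. The other 18 points, about four in five of such gaps (18/23), would be reported as no difference.

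**The case against.** **The harm is limited.** No section makes an outcome analysis depend on these tests, the Cox covariates are fixed beforehand, and the primary objective is feasibility. This stands. A reader might infer that the tests will steer adjustment or bias the treatment comparison, but the protocol does not say so.

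**Spurious differences are not shown to be likely.** This also stands. The 68% needs an unstated 0.05, independence, separate testing of every named condition, and full 5% size in every test. The exact sizes contradict the last of these.

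**The Chi-squared test is not shown to be invalid here.** A reader might take the small expected counts to mean inflated false alarms. The sizes of 0.2% to 6.4% show a test that is mostly conservative. The wording also leaves some choice of test, and a small-sample variant could properly sit in an analysis plan.

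**Lack of power against a real imbalance is the wrong charge.** One might want to quote the test's power for a true 0.5 SD imbalance. Under sound randomisation there is no systematic imbalance to detect, so that figure would contradict the argument. The relevant quantity is the size of chance gap that goes unflagged.

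**The tests could serve as a check on allocation.** Staff are unblinded and allocation uses envelopes, so subversion is conceivable. But section 8.1 gives no such purpose; it presents the tests as the means of establishing differences.

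**Conclusion.** The point holds as a minor one. Section 8.1 fixes by name a procedure that cannot do what it is said to do under the allocation in section 6.1.1.

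At an assumed 0.05, the odds of at least one chance difference are roughly even: 46% to 68% nominally for 12 to 22 independent tests, and lower once small cells are allowed for. The 0.85 SD threshold for continuous characteristics assumes 12 in each arm and the same 0.05. False reassurance is at least as serious as false alarm. The consequence is confined to interpretation of the baseline table and, through it, of the leg-volume result.

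**What to change.** In section 8.1, replace the closing sentence with: *Baseline characteristics will be summarised by arm as n (%), mean (SD) or median (IQR), without significance tests.* This costs one sentence, removes 12 to 22 uninformative p-values, and leaves sample size, data collection and outcome analyses unchanged.

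Separately, amend sections 8.2 and 8.3 so that the leg-volume comparison is adjusted for week 0 leg volume regardless of observed balance. ANCOVA would do, or a rank-based version if the distribution requires it. Week 0 leg volume is already scheduled (Table 3), so no new data are needed, and precision should improve at almost no cost. This is not free of consequence: it replaces or supplements the unadjusted Mann-Whitney or t-test. It therefore has to be written into sections 8.2 and 8.3, because a sentence in 8.1 alone would contradict them.

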#### 8.2 **Primary outcome statistics**

The primary objective for this pilot study was the feasibility of conducting a larger scale randomised controlled trial. The secondary outcome statistics are other clinical and patient related outcomes measures.

The following descriptive statistics will be reported on:

- Number of patients screened
- Number of patients eligible/ineligible, and percentage of patients consented into the trial
- Number of patients completed the trial/discontinued (plus reasons if discontinued)

Lymphoedema control: Mann-Whitney U-test of change in leg volume (week 0 vs 12) between control and StepIt groups respectively.

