#### 1. LAY SUMMARY

Chronic lymphoedema is a long-term medical condition that results in swelling of the limbs or other body parts. The cause of fluid build-up in particularly the arms and/or legs is problems with the lymphatic system, which is a network of glands and vessels that helps fight infection and remove excess liquid in the body. Lymphoedema of the legs is common in people who: may have another chronic condition such as heart failure, COPD, or vascular disease; are inactive for long periods; are overweight or obese; or have had cancer treatment to eg the pelvis. Oedema is a risk factor for serious complications such as cellulitis infection. There is some evidence to suggest that specific resistance exercise of the calf muscle – moving the front of the foot up and down by plantar flexion, similar to what a drummer does when using the foot pedal of a drum - may improve the calf muscle pump function and help reduce fluid build-up. It has been shown that at least in the short-term there is better blood flow and endurance if the calf muscle is exercised in this manner.

As yet there remains considerable uncertainty as to the effects of an exercise programme on leg lymphoedema symptom control. There is very limited research data available on the medium- to long-term effects of calf muscle exercising by lymphoedema patients on the volume of the legs. This study is a prospective, controlled, randomised, feasibility trial to determine if the use of a CEapproved plantar flexion pedal, developed by StepIt Ltd, will be of benefit to people with lymphoedema of the leg. This study initially aimed to assess the feasibility of conducting a full randomised clinical trial in the future. After analysis of results from data involving an initial 24 patients, one outcome measure will be change in leg volume at 6 and 12 weeks. Other outcome measures will include acceptability of use of the device, trial completion rates, and lymphoedemarelated quality of life. Due to the swelling experienced by leg lymphoedema patients, physical activity may be hard to achieve for some patients. Initiating calf muscle exercises whilst sitting down may be a first step in increasing physical activity for this population and improving calf muscle pump function.

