#### Trial-related outcome measures

- Participants' compliance to StepIt exercise regime
- Recruitment and attrition rates, willingness of patients to be randomised, response rates to questionnaires, and degrees of missing data
- Testing of eligibility criteria and ability/willingness of clinical staff to partake in recruitment of participants

- Ability of site and clinicians to recruit and randomise patients, irrespective of care setting
- To assess any training requirements
- Adequacy of duration of follow-up (e.g. in relation to lymphoedema management and outcomes)
- Fitness for purpose of data collection methods including across and between care settings
- Adverse events

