#### 5.5.2 Secondary outcome measures

The primary outcome for this pilot trial will be the feasibility of conducting a full RCT in the future. However, this study also aims to provide preliminary results regarding the acceptability and efficacy of a simple StepIt pedal as an adjuvant therapy for lymphoedema symptom control.

Clinical outcome measures

- Leg volume (see notes below), at week 0, 6, 12
  - Measured only between 9.30am to 3.30pm
  - Where possible the same rater is used for each participant; name of rater will be recorded.
- Ankle circumference measurement, using lateral malleolus as reference point (Brodovicz et al, 2009), at week 0, 6, 12
- Clinician's oedema severity score (Table 4 below; Nieman et al, 2013)

Table 4.	Clinician's	oedema	severity	/ score
TUDIC T,	chinciun 5	ocucina	JUVUII	, 20010

	0	1+	2+	3+	4+
Visible	No	yes	yes	yes	yes
Pitting	No	slight	>slight	>slight	'can't reach tibia'
Level	n/a	n/a	< knee	>knee	>knee

- Ankle range of motion (using goniometer)
- Pain score, at week 0, 6, 12
- Quality of life score, determined with EQ-5D-5L and LYMQOL-L Questionnaire, at week 0, 6, 12
- Participant opinion on trial participation, at week 12 (StepIt users only)
- Patient withdrawal rates due to change in management (e.g. need for surgery, hospital admission, infection, or other)
- Leg infection rates, primarily cellulitis

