#### 6.3 Early withdrawal of subjects + intervention suspension

Patients have the right to withdraw from the trial at any time and without giving any reason. If a patient withdraws from the trial, any and all information gathered prior to the withdrawal will be included in the analysis, but no further data collection will occur. If a patient does not attend a planned follow-up appointment then two more attempts will be made to contact the patient regarding the study. If still no contact can be made then the patient is deemed lost to follow-up and any collected study data will be retained.

If a patient needs to suspend the StepIt exercises then this does not change the planned follow-up dates for 6 and 12 weeks after baseline study visit. This may be eg hospital admission. If a patient develops an infection then the routine approach will be: rest of the legs (ie no StepIt exercises) for duration of antibiotics course + 1 week. Intervention suspension events will be recorded.

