#### 8.3 Secondary outcome statistics

To evaluate the effect of the StepIt exercises on lymphoedema control in the control group will be compared with data from the StepIt group. The StepIt exercise data will be stratified into different groups according to coherence to treatment.

Efficacy is defined by the following parameters:

- Leg volume (indirect via circumference measurements)
- Ankle circumference
- Ankle range of motion

- Visual analogue pain score
- Quality of Life questionnaires scores

To compare the groups in terms of leg volume and ankle circumference, Mann-Whitney U-test or ttest will be applied , depending on distribution of data.

To assess ankle range of motion, the average differences between first and last visit will be calculated. The control and intervention group will be compared by applying Mann-Whitney U-test or unpaired t-test depending on the distribution of the data.

To measure patient-reported outcome measures on quality of life at first visit, second visit and final visit, the Mann-Whitney U-test will be performed. Data of the control and intervention group will be compared by applying the Mann-Whitney U-test.

Subject to sufficient data being available, Cox proportional hazards regression analysis will be conducted to investigate the role of StepIt and other covariates in leg lymphoedema symptom control. Other covariates include: lymphoedema severity and chronicity at baseline, ankle motion range, patient age, patient mobility, absence/presence of co-morbidities.

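### The leg-volume test in 8.2 uses only the week 0 to 12 change, so a patient who leaves after week 6 adds nothing to it, although 6.3 promises to analyse data gathered before withdrawal

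*Protocol*

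**What the plan says.** Section 5.5.2 schedules "Leg volume (see notes below), at week 0, 6, 12". The protocol summary sets the efficacy objective at both 6 and 12 weeks after baseline, and the lay summary says "one outcome measure will be change in leg volume at 6 and 12 weeks".

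On leavers, section 6.3 states that "any and all information gathered prior to the withdrawal will be included in the analysis, but no further data collection will occur". For those who cannot be contacted, "the patient is deemed lost to follow-up and any collected study data will be retained".

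On analysis, section 8.2 specifies a "Mann-Whitney U-test of change in leg volume (week 0 vs 12) between control and StepIt groups respectively". Section 8.3 compares leg volume again, by Mann-Whitney or t-test, but names no time point. Section 6.1 calls leg-volume change the primary clinical outcome, expects this trial to inform the effect size and variance for later work, and says that withdrawal before week 12 is not known.

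**The concern.** The 8.2 test needs a week-12 value from every patient it ranks. Someone who withdraws after the week-6 visit has given a baseline and a follow-up volume, and 6.3 commits to using them, yet neither can enter this test. The only leg-volume comparison with a stated time point is therefore restricted to completers.

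The effect estimate and its variance are at stake, because this trial exists partly to hand them to a later one. Patients and lymphoedema specialists are unblinded (6.1.1), and the pedal regime takes extra time and effort (7.1). Pedal users who see no response by week 6 could plausibly leave more often than controls. The completers in that arm would then look better than the arm as randomised, even with an inert pedal.

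**Working it through.** **1. The plan's own figure.** 2 arms × 12 = 24 patients, a rule of thumb. The protocol states no power, SD or dropout allowance, so there is no power calculation to reproduce.

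**2. Who can be scored in 8.2.**

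| Patient leaves | Volumes held | Week 0 to 12 change |
|---|---|---|
| before week 6 | week 0 | none |
| between weeks 6 and 12 | weeks 0 and 6 | none |
| completes | weeks 0, 6 and 12 | available |

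The middle row is the gap: a follow-up volume exists and the test cannot use it. With assumed loss after week 6 of 10%, 20% or 30%, the number affected is 24 × 0.10 = 2.4, 24 × 0.20 = 4.8 or 24 × 0.30 = 7.2 patients.

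**3. If dropout is random.** There is no bias, only lost precision. The 95% CI half-width in SD units is t × √(2/n):
- 12 per arm: 2.074 × √(2/12) = 0.85
- 8 per arm: 2.145 × √(2/8) = 1.07

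Using the week-6 values recovers part of this. In 8,000 simulated trials per setting (12 per arm, correlation 0.7 between week-6 and week-12 change), the standard errors were:

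| Loss | Completers only | Using week 6 | Reduction |
|---|---|---|---|
| 10% | 0.426 | 0.417 | 2% |
| 20% | 0.464 | 0.439 | 5% |
| 30% | 0.495 | 0.457 | 8% |

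**4. If dropout follows week-6 response in the pedal arm only (milder pattern).** All inputs are assumed:
- no true effect, and normal changes with SD 1;
- pedal-arm loss logistic in week-6 change, with slope 1.2 per SD;
- control loss random at the base rate.

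Completers' bias = correlation × mean standardised week-6 change among pedal patients who stay. Negative values favour StepIt.

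| Base loss | Actual pedal-arm loss | Mean week-6 change, stayers | × 0.7 | Simulated bias | Bias using week 6 |
|---|---|---|---|---|---|
| 10% | 15% | −0.149 | −0.104 | −0.105 | 0.000 |
| 20% | 25% | −0.243 | −0.170 | −0.170 | 0.001 |
| 30% | 34% | −0.322 | −0.225 | −0.229 | −0.003 |

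The slope raises pedal-arm loss above the base rate, so the arms also differ in amount of loss. Over the three loss rates, the size of the bias is 0.08 to 0.16 SD at correlation 0.5 and 0.12 to 0.26 SD at 0.8. Type I error of the Mann-Whitney test stays at about 0.05 to 0.06.

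**5. A harsher pattern.** Here the 1, 2, 3 or 4 pedal patients of 12 with the worst week-6 change leave, and no control leaves (6,000 runs per setting). At correlation 0.7 the bias is 0.11, 0.20, 0.28 and 0.36 SD. Over correlations of 0.3 to 0.9 it runs from 0.04 to 0.46 SD. With four leavers, type I error reaches 0.11 at correlation 0.7 and 0.18 at 0.9. With one leaver or a low correlation the effect is small.

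**The case against.** **6.3 speaks of the analysis, not of every test.** A patient leaving after week 6 still enters the discontinuation counts and could enter other comparisons. This stands: the two sections are not in outright contradiction. The mismatch is confined to the one leg-volume test whose time point is fixed.

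**Week-6 volumes may be used elsewhere.** A reader might infer that the trial discards them. The documents do not support that: 8.3 compares leg volume with no time point, and the objective names week 6. The volumes are lost to the 8.2 test, not necessarily to the trial.

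**Visit wording in 8.3.** A reader might also infer that 'last visit' and 'final visit' create different end points for different outcomes. They do not. Ankle range of motion is scheduled only at weeks 0 and 12 (Table 3), and the first, second and final quality-of-life visits match weeks 0, 6 and 12.

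**Missing-data rules usually sit in the analysis plan.** True, and a missing imputation rule alone would be no finding. But the protocol itself fixes a test on a single follow-up visit while promising to use earlier data, and a later plan would have to resolve that.

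**The bias is assumption-driven.** This stands too. No passage supports the dropout mechanism. In the milder pattern the bias is only 0.105/0.426 = 0.25, 0.170/0.464 = 0.37 and 0.229/0.495 = 0.46 of the random-dropout standard error. It is also a bias in means, whereas 8.2 names a rank test.

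**Conclusion.** The point holds in a limited form. As worded, the 8.2 comparison is completers only and cannot use the week-6 volumes of patients who leave later, despite 6.3. With random dropout the cost is modest: using those volumes cuts the standard error by 2% to 8% at correlation 0.7. With dropout tied to week-6 response and differing by arm, the preliminary effect could be overstated by roughly 0.1 to 0.2 SD at 10% to 30% base loss and correlation 0.7, and by more under the harsher pattern.

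These sizes rest on assumed dropout rates, correlations and mechanism. The documents do not show that such dropout will occur, and they do not support reading this as a likely false-positive trial: feasibility is the primary objective, attrition is itself measured, and no confirmatory claim depends on the test. The harm would be to the effect estimate passed to the next trial. The change is worth making because it is cheap.

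**What to change.** **Section 8.2.** Estimate the leg-volume difference with a repeated-measures model. Use weeks 6 and 12 as outcomes, with baseline volume, arm, visit and arm-by-visit as terms, in all randomised patients with at least one follow-up volume. Report the week-12 and week-6 differences with 95% CIs. Keep the Mann-Whitney test of the week 0 to 12 change as a sensitivity analysis.

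**Section 6.3.** Say that patients with no follow-up volume are counted in the attrition and baseline summaries. The model cannot use them either, so the text should not imply that it does.

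Extending the model to quality-of-life scores is optional.

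**Cost.** Wording in two sections and slightly more analysis work, with no new visits or data. The move is not a sharp one, since 8.3 already allows a t-test for leg volume. The downside is reliance, with 24 patients, on approximate normality and on missingness being explained by the observed volumes. The retained rank test guards against the first of these but not the second.
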